9.7.1.3 Subject Disposition

The number (percentage) of treated subjects will be summarized as well as subjects who completed the study/discontinued from the study and reasons for discontinuation by treatment cohort.

9.7.1.4 Demographic and Other Baseline Characteristics

Demographic and other baseline characteristics for the FAS will be summarized for each treatment cohort and all treatment cohorts combined using descriptive statistics. Continuous demographic and baseline variables include age, sex, race, region, ECOG-PS, NYHA cardiac disease classification, and pTNM staging.

9.7.1.5 Prior and Concomitant Therapy

All investigator terms for medications recorded in the CRF will be coded to an 11-digit code using the World Health Organization Drug Dictionary drug codes. Prior medications will be defined as medications that stopped before the first dose of study drug. Concomitant medications will be defined as medications that (1) started before the first dose of study drug and were continuing at the time of the first dose of study drug, or (2) started on or after the date of the first dose of study drug up to 30 days after the subject's last dose. All medications will be presented in subject data listings.

9.7.1.6 Efficacy Analyses

All efficacy analyses that are conducted at the end of the Treatment Phase will be based on the Full Analysis Set. Selected efficacy analyses may be performed if needed for subjects with the combination of lenvatinib and pembrolizumab as the first line treatment versus other subjects with prior systemic therapies. For the renal cell carcinoma cohort, efficacy subgroup analyses may be presented for treatment naïve subjects, subjects who were previously treated with an anti-PD-1/PD-L1 therapy, and subjects who were previously treated without an anti-PD-1/PD-L1 therapy.

9.7.1.6.1 PRIMARY EFFICACY ANALYSIS

The primary efficacy endpoint in Phase 2 is $ORR_{(Week\ 24)}$ based on irRECIST. Estimated $ORR_{(Week\ 24)}$ and the exact 95% (CI) using the method of Clopper–Pearson will be presented. The primary efficacy analysis of each cohort will be performed when all subjects in that cohort have completed 8 cycles of treatment, discontinued due to disease progression, developed unacceptable toxicity, subject choice, withdrew consent, lost to follow up or the study is terminated by the sponsor.

9.7.1.6.2 SECONDARY EFFICACY ANALYSES

The following secondary efficacy analyses will be performed on the data collected from the

Phase 2 portion of the study for each treatment cohort.

ORR: ORR and corresponding 95% CI based on exact binomial distribution will be estimated for each treatment cohort.

PFS: The distribution of PFS will be estimated using Kaplan–Meier methodology. Median time to PFS and 95% CI will be provided for each treatment cohort. Three-month, 6-month, 9-month, and 1-year PFS rate will be estimated using the Kaplan–Meier method and corresponding 95% CIs will be provided.

OS (overall survival): All events of death will be included, regardless of whether the event occurred while the subject was still taking study drug, or after the subject discontinued study drug. If a subject has no record of death, then the data will be censored at the date the subject was last known to be alive, or the data cutoff date, whichever is earlier. The distribution of OS will be estimated using Kaplan–Meier methodology. Median survival time and the corresponding 95% CI, survival rates at 12, 18, and 24 months, and corresponding 95% CIs will be estimated using Kaplan–Meier method for each treatment cohort.

DCR: Disease control rate and exact 95% CI will be estimated for each treatment cohort.

CBR: Clinical benefit rate and exact 95% CI will be estimated for each treatment cohort.

DOR: The distribution of the duration of response will be estimated using Kaplan–Meier Methodology. Median DOR and 95% CI will be provided for each treatment cohort.

Durable SD rate: DSDR and exact 95% CI will be estimated for each treatment cohort.

9.7.1.6.3 EXPLORATORY EFFICACY ANALYSES

The tumor response endpoints will be explored based on modified RECIST 1.1 assessments, and will be summarized and listed by cohort. No statistical comparison will be performed between irRECIST and modified RECIST 1.1 results.

The tumor response endpoints will also be evaluated for the subject in the endometrial and renal cell carcinoma analysis sets using IIR assessment using irRECIST, modified RECIST 1.1, and RECIST v1.1 as exploratory analyses. A concordance analysis will be performed comparing IIR and investigator assessments.

Blood and tumor biomarkers which correlate with efficacy endpoints will be explored.

9.7.1.7 Pharmacokinetic, Pharmacodynamic, Pharmacogenomic, and Other Biomarker Analyses

9.7.1.7.1 PHARMACOKINETIC ANALYSES

To assess any drug–drug interaction between lenvatinib and pembrolizumab, the dose-normalized PK profile for lenvatinib in combination with pembrolizumab from this study

will be compared graphically to that from patients with different tumor types from completed studies receiving lenvatinib monotherapy.

9.7.1.7.2 PHARMACODYNAMIC, PHARMACOGENOMIC, AND OTHER BIOMARKER ANALYSES

The effect of lenvatinib-pembrolizumab combination therapy on soluble, tissue, genetic and/or imaging biomarkers will be summarized using descriptive statistics using the pharmacodynamic analysis set.

9.7.1.8 Safety Analyses

All safety analyses will be performed on the Safety Analysis Set. Safety data, presented by treatment cohorts, will be summarized on an “as treated” basis using descriptive statistics (eg, n, mean, standard deviation, median, minimum, maximum for continuous variables; n [%] for categorical variables). Safety variables include treatment-emergent adverse events (TEAEs), clinical laboratory parameters, vital signs, 12-lead ECG results, and echocardiogram results, including LVEF. Study D1 will be defined as the date of administration of the first dose of study drug.

Selected safety analyses may be performed if needed for subjects with the combination of lenvatinib and pembrolizumab as the first line treatment versus other subjects with prior systemic therapies. For the renal cell carcinoma cohort, safety subgroup analyses may be presented for treatment naïve subjects, subjects who were previously treated with an anti-PD-1/PD-L1 therapy, and subjects who were previously treated without an anti-PD-1/PD-L1 therapy.

9.7.1.8.1 EXTENT OF EXPOSURE

The number of cycles/days on treatment, quantity of study drug administered, and the number of subjects requiring dose reductions, treatment interruption, and treatment discontinuation due to AEs will be summarized.

9.7.1.8.2 ADVERSE EVENTS

The AE verbatim descriptions (investigator terms from the CRF) will be classified into standardized medical terminology using the Medical Dictionary for Regulatory Activities (MedDRA). Adverse events will be coded to the MedDRA lower level term closest to the verbatim term. The linked MedDRA preferred term (PT) and primary system organ class (SOC) are also captured in the database.

A TEAE is defined as an AE that emerges during treatment, having been absent at pretreatment (Baseline) or

- Reemerges during treatment, having been present at pretreatment (Baseline) but stopped before treatment, or

- Worsens in severity during treatment relative to the pretreatment state, when the AE is continuous.

Only those AEs that are treatment-emergent will be included in summary tables. All AEs, treatment-emergent or otherwise, will be presented in subject data listings.

The TEAEs will be summarized by treatment cohort. The incidence of TEAEs will be reported as the number (percentage) of subjects with TEAEs by SOC and PT. A subject will be counted only once within an SOC and PT, even if the subject experienced more than 1 TEAE within a specific SOC and PT. The number (percentage) of subjects with TEAEs will also be summarized by highest CTCAE grade.

The number (percentage) of subjects with TEAEs will also be summarized by relationship to study drug (Yes [related] and No [not related]).

Treatment-related TEAEs include those events considered by the investigator to be related to study treatment. The number (percentage) of subjects with treatment-related TEAEs will also be summarized by highest CTCAE grade).

Adverse events will be summarized using the Safety Analysis Set. The number of AEs and number and incidence (%) of subjects with AEs will be summarized by cohort/dose level and overall. To obtain the incidence (%), the number of subjects with at least 1 event and the percentage of subjects with AEs by SOC and by PT will be calculated. Incidence (%) by causal relationship with study drug and by severity (CTCAE v4.03) will also be calculated. For clinically significant events, time of onset and recovery will be reported.

Adverse events will be summarized by the following subgroups: age (≤ 65 years, >65 years), sex (male, female), and race (white, black, other) if necessary.

The number (percentage) of subjects with TEAEs leading to death will be summarized by MedDRA SOC and PT for each cohort. A subject data listing of all AEs leading to death will be provided.

The number (percentage) of subjects with treatment-emergent serious adverse events (SAEs) will be summarized by MedDRA SOC and PT for each cohort. A subject data listing of all SAEs will be provided.

The number (percentage) of subjects with TEAEs leading to discontinuation from study drug will be summarized by MedDRA SOC and PT for each cohort. A subject data listing of all AEs leading to discontinuation from study drug will be provided.

9.7.1.8.3 LABORATORY VALUES

Laboratory results will be summarized using Système International units, as appropriate. For all quantitative parameters listed in [Section 9.5.1.5.3](#), the actual value and the change from baseline to each postbaseline visit and to the end of treatment will be summarized by visit and treatment using descriptive statistics. Qualitative parameters listed in [Section 9.5.1.5.3](#)

will be summarized using frequencies (number and percentage of subjects), and changes from baseline to each postbaseline visit and to the end of treatment will be reported using shift tables. Percentages will be based on the number of subjects with both nonmissing baseline and relevant postbaseline results.

Laboratory parameters will be categorized according to CTCAE v4.03 grades, and shifts from baseline CTCAE grades to maximum and final postbaseline grades will be assessed. CTCAE v4.03 will be used to identify subjects with treatment-emergent markedly abnormal laboratory values (TEMAV). A more detailed definition of TEMAV will be specified in the SAP. A summary of TEMAVs will be presented by visit and overall and by treatment group.

9.7.1.8.4 VITAL SIGNS

Descriptive statistics for vital signs parameters (ie, systolic and diastolic BP, resting HR, respiratory rate, temperature, and weight) and changes from baseline will be presented by visit and treatment cohort.

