During the Treatment Period, both in the Treatment Phase and in the Extension Phase, subjects with systolic BP ≥ 160 mm Hg or diastolic BP ≥ 100 mm Hg must have their BP monitored on Day 15 or more frequently as clinical indicated until systolic BP has been ≤ 150 mm Hg and diastolic BP has been ≤ 95 mm Hg for 3 consecutive months. If a repeat event of systolic BP ≥ 160 mm Hg or diastolic BP ≥ 100 mm Hg occurs, the subject must resume the Day 15 evaluation until systolic BP has been ≤ 150 mm Hg and diastolic BP has been ≤ 95 mm Hg for 3 consecutive months.

The following guidelines should be followed for the management of systolic BP ≥ 160 mm Hg or diastolic BP ≥ 100 mm Hg confirmed on repeat measurements after 1 hour:

1. Continue lenvatinib and institute antihypertensive therapy for subjects not already receiving antihypertensive medication
2. For those subjects already on antihypertensive medication, dose of the current agent may be increased, if appropriate, or 1 or more agents of a different class of antihypertensive should be added.
3. If systolic BP ≥ 160 mm Hg or diastolic BP ≥ 100 mm Hg persists despite maximal antihypertensive therapy, then lenvatinib administration should be interrupted. It should be restarted at one lower dose level as specified in [Table 3](#) only when systolic BP ≤ 150 mm Hg and diastolic BP ≤ 95 mm Hg and the subject has been on a stable dose of antihypertensive medication for at least 48 hours

- If systolic BP ≥ 160 mmHg or diastolic BP ≥ 100 mmHg recurs on the first dose reduction despite optimal management of hypertension with antihypertensive medications (either by dose increase or the addition of a different class of antihypertensive), then lenvatinib administration should be interrupted. It should be restarted at an additional dose reduction as specified in [Table 3](#) only when systolic BP ≤ 150 mmHg and diastolic BP ≤ 95 mmHg and the subject has been on a stable dose of antihypertensive medication for at least 48 hours.

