- r. Collection of blood sample to obtain plasma, serum, or other components to be used for biomarker studies. Samples will be obtained at baseline, C1D15, D1 of all subsequent cycles up to and including C18, and at the off-treatment assessment.
- s. Subjects with NSCLC require a newly obtained tumor biopsy for biomarker analysis which must be obtained prior to the first dose. If an archival tumor sample for biomarker analysis is not available from subjects with RCC, EC, UC, M, or HNSCC, then a newly obtained tumor biopsy must be obtained prior to the first dose. If a newly obtained biopsy is required, it is preferred that the biopsy is obtained from a non-target lesion. Subjects must have recovered adequately from the biopsy prior to starting therapy.
- t. Concomitant meds are recorded for 30 days after last dose.
- u. The off-treatment assessment should occur within 30 days after the final dose of study treatment.
- v. Survival data will be collected every 12 weeks until end of Treatment Phase (when subjects move into Extension Phase). All anticancer therapy will be recorded until time of death or termination of survival follow up. As of Amendment 09, the Follow-up Period will consist of the Off-Tx Visit. No further visits will be conducted. The sponsor has decided to terminate survival follow-up for all subjects currently in survival follow-up. Survival follow-up data will no longer be collected after the Off-Treatment Visit and after 30 days from the last dose of study drugs.
- w. Subjects with systolic BP ≥ 160 mmHg or diastolic BP ≥ 100 mmHg must have their BP monitored on D15 or more frequently as clinically indicated until systolic BP has been ≤ 150 mmHg and diastolic BP has been ≤ 95 mmHg for 3 consecutive months. If a new event of systolic BP ≥ 160 mmHg or diastolic BP ≥ 100 mmHg occurs, the subject must resume the Day 15 evaluation until systolic BP has been ≤ 150 mmHg and diastolic BP has been ≤ 95 mmHg for 3 consecutive months.
- x. Urine dipstick testing for subjects with proteinuria $\geq 2+$ should be performed on Day 15 or more frequently as clinically indicated until the results have been 1+ or negative for 3 consecutive months. If a new event of proteinuria $\geq 2+$ occurs, the subject must resume the Day 15 urine dipstick testing for evaluation of proteinuria until results are 1+.

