 - d. Assessments will include vital signs (resting BP, HR, RR, and body temperature), weight, and height. Height will be measured at the Screening Visit only. Elevated BP assessment (ie, systolic BP ≥ 140 mmHg or diastolic BP ≥ 90 mmHg) should be confirmed by a repeat assessment after a minimum of 1 hour. One BP assessment is defined as the mean value of 3 measurements at least 5 minutes apart. Subjects with systolic BP ≥ 160 mmHg or diastolic BP ≥ 100 mmHg must have their BP monitored every 2 weeks (on Day 1 and Day 15 or more frequently, as clinically indicated) until systolic BP has been ≤ 150 mmHg and diastolic BP has been ≤ 95 mmHg for 3 consecutive months. If a new event of systolic BP ≥ 160 mmHg or diastolic BP ≥ 100 mmHg occurs, the subject must resume the Day 15 evaluation until systolic BP has been ≤ 150 mmHg and diastolic BP has been ≤ 95 mmHg for 3 consecutive months. As of Amendment 09, weight and body temperature will be assessed as clinically indicated in the Extension Phase.
 - e. A physical examination will be performed at the Screening or Baseline Visit, on C1D15, on D1 of each subsequent cycle, and at the Off-Tx Visit assessment. A symptom-directed physical examination will be performed on C1D1 and at any time during the study, as clinically indicated. As of Amendment 09, oral examination will be included
 - f. Required if screening physical examination was performed >7 days prior to C1D1.
 - g. Single, 12-lead ECG. Subjects must be in the recumbent position for a period of 5 min prior to the ECG. During the Treatment and Extension Phases, ECGs will be collected every cycle.
 - h. Phone contact will take place on Day 8 (± 2 days) of C1 to assess subjects for development of early toxicity. An unscheduled visit will occur prior to C1D15 if deemed necessary by the investigator.
 - i. Clinical laboratory tests will be performed by the local laboratory. Assessments should be performed within 72 h prior to the visit. Clinical chemistry and hematology results must be reviewed prior to administration of study drug on C1D1 and within 48 hours after receiving quick estimation. If there is \geq Grade 3 clinical significant hematologic or clinical chemistry toxicity, repeat laboratory test and AEs assessment at least every 7 days (until improvement to $<$ Grade 3). Thyroid function will be assessed every 2 Cycles (C3D1, C5D1, etc.).

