5.6.5 Vital Signs

Vital sign values will be evaluated on an individual basis by subject. Descriptive statistics for vital signs parameters (diastolic and systolic blood pressure, resting HR, respiratory rate, body temperature, and weight) and changes from baseline will be presented.

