8 DEFINITIONS AND CONVENTIONS FOR DATA HANDLING

Study Day 1

Study Day 1 is defined as the day of the first dose of study drug administered.

Baseline

Baseline is defined as a Day 1 pre-dose, the last observation before the start of drug, if the Day 1 pre-dose is missing.

By-visit analyses

All by-visit analyses will be performed using assessments at corresponding scheduled visits recorded in the eCRF. For shift tables, all post-baseline assessments including those at scheduled and unscheduled visits will be used.

Incomplete dates

For incomplete dates involving efficacy and safety data, see [Section 5.3.4](#) for data handlings.

Limit of Quantification (BLQ) in pharmacokinetics analyses

When calculating the mean or median value for the concentrations at a given time point, the BLQ values will be assigned as zero. If the proportion of values reported as BLQ is more than 50%, no summary statistics should be represented at that time point, and the value will be treated as missing in mean or median concentration profiles.

More specific details, if any, are given with the discussion of analyses for each endpoint. Details on the way that BLQ values will be replaced will be described in a separate plan detailing the analyses.

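### From Cycle 2, Day 15 blood pressure is required only in subjects who reached systolic 160 or diastolic 100 mmHg, yet by-visit tables would list it in sequence with Day 1 values from the whole cohort

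*Protocol*

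**What the plan says.** **Schedule.** Protocol Tables 8 and 9 mark vital signs for every subject at Baseline, Cycle 1 Day 1, Cycle 1 Day 15, Day 1 of each later cycle and the Off-Tx visit. From Cycle 2 the Day 15 columns are numbered visits (7, 9, 11, 13 and so on; 21, 23, 25 and so on in the Phase 2 Extension Phase). Their vital-sign and urine dipstick marks carry footnotes.

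**Who is measured on Day 15.** Table 8 footnote w says that subjects with systolic BP of at least 160 or diastolic BP of at least 100 mmHg "must have their BP monitored on D15 or more frequently as clinically indicated". Table 9 footnote d says that such subjects "must have their BP monitored every 2 weeks (on Day 1 and Day 15 or more frequently, as clinically indicated". Section 9.4.1.1.2 has them "must have their BP monitored on Day 15 or more frequently as clinical indicated". Monitoring ends once BP has been at or below 150/95 mmHg for 3 consecutive months. After a new event, "the subject must resume the Day 15 evaluation until systolic BP has been" back under control.

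**Analysis.** Protocol 9.7.1.8.4 presents vital signs by visit: "changes from baseline will be presented by visit and treatment cohort". SAP section 8 says: "All by-visit analyses will be performed using assessments at corresponding scheduled visits recorded in the eCRF". SAP 5.6.5 says: "Vital sign values will be evaluated on an individual basis by subject", followed by descriptive statistics and changes from baseline. It does not mention visits. SAP section 7 declares no change to the planned analyses.

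**The concern.** A by-visit table is read down the page as the course of one group over time. Here the group changes from row to row. The Day 1 rows hold everyone still on treatment. The Day 15 rows from Cycle 2 hold subjects chosen because the variable being summarised was high at some point.

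Protocol 9.4.1.1.2 treats hypertension as a recognised effect of this drug class, so these tables will be read. A reader could take a difference between adjacent rows for a drug or dosing-cycle effect when it comes from who was measured. Change from baseline is affected too. Eligibility requires BP of at most 150/90 at screening, so anyone who enters Day 15 monitoring has had a reading at least 10 mmHg above one of those limits (160 - 150 or 100 - 90).

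**Working it through.** The plan states no figure for this point, so there is nothing to reproduce. The check has three steps.

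**Step 1. How many rows are affected.** The Phase 2 Treatment Period after Cycle 1 covers Cycles 2 to 8, that is 8 - 2 + 1 = 7 cycles, each with one Day 1 and one Day 15 column. Seven of those 14 visits are therefore conditional, in strict alternation with the unconditional ones. The pattern continues from Cycle 9. In Phase 1b it also starts at Cycle 2. This much follows from the schedule alone.

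**Step 2. What the switch does to the mean.** Let f be the fraction under Day 15 monitoring, mF their mean and mU the mean of the rest.

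- Day 1 mean = f × mF + (1 - f) × mU
- Day 15 mean = mF
- Difference = (1 - f) × (mF - mU)

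The documents give none of these inputs. Taking f from 5% to 40% and a gap of 5 to 20 mmHg as assumptions:

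- smallest: 0.60 × 5 = 3 mmHg
- middle: 0.80 × 15 = 12 mmHg
- largest: 0.95 × 20 = 19 mmHg

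The sign is that of mF - mU. If management takes the subset below the rest, the Day 15 row falls.

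**Step 3. How far management could move it.** The entry and exit rule was simulated for systolic BP only, in 20,000 subjects over Cycles 2 to 12. Assumed inputs were an on-treatment mean of 130 or 135 mmHg, between-subject SD of 10 or 12 and within-subject SD of 8 to 12. A Day 1 reading of at least 160 started monitoring and triggered a fixed, lasting reduction. Five consecutive Day 1 readings of at most 150 (roughly 3 months) ended monitoring.

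| Assumed BP reduction (mmHg) | Input sets run | Day 15 mean minus Day 1 mean (mmHg) |
|---|---|---|
| 0 | 1 | +20.5 to +24.0 |
| 10 | 2 | +9.4 to +14.2 |
| 20 | 4 | -5.6 to +4.2 |
| 30 | 2 | -15.9 to -6.0 |

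At the cycles printed (2, 3, 6 and 10), the Day 15 rows rested on about 2% to 13% of subjects. The population switch is present in every scenario; the direction and size of the difference are not constant.

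**The case against.** **The SAP does not say that vital signs are by visit.** This is correct. SAP 5.6.5 omits the words, whereas 5.6.6 on ECGs uses them and 5.6.4 on laboratory values uses them conditionally. Protocol 9.7.1 leaves detail to the SAP, and the programming rules and table shells, where a visit filter might sit, are separate documents not available here. The link therefore rests on Protocol 9.7.1.8.4 together with SAP section 8. It stands because 5.6.5 offers no other rule for which readings enter the statistics and section 7 declares no departure from the protocol. Pooling all readings instead would over-weight the hypertensive subset.

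**A false rise at every Day 15 row.** A reader might infer that the alternation forces mean BP up at each Day 15 and down at the next Day 1. The documents do not support that. Section 9.4.1.1.2 requires antihypertensive treatment to be started or intensified, and lenvatinib to be interrupted if the elevation persists. Day 15 checks also continue through 3 months of control, so some subjects measured there are already controlled. As the table shows, the sign can reverse.

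**Other vital signs.** A reader might extend the point to heart rate, weight and temperature. The Day 15 rule asks for BP only, and as of Amendment 09 weight and temperature in the Extension Phase are taken as clinically indicated. There is no basis for making these part of the main point.

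**Low impact.** The study is single-arm, these tables carry no test or decision rule, and n is shown. Adverse event summaries by grade and by action taken are unaffected. This limits the importance of the point but does not remove it: a small n looks like missed visits and does not reveal selection on BP.

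**Conclusion.** The concern holds in limited form. As written, by-visit BP rows from Cycle 2 on alternate between all treated subjects and a subset selected on BP, so the Day 15 means and changes from baseline do not describe the cohort. That conclusion rests on the schedule, Protocol 9.7.1.8.4 and SAP section 8, and on reading SAP 5.6.5 as not withdrawing the by-visit presentation.

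The size is not determined by the documents. A higher Day 15 mean is the natural expectation unless management brings the subset close to or below the rest. The range of about +24 to -16 mmHg comes entirely from the assumed distributions and reductions, ignores the diastolic criterion and should not be read as a forecast.

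The consequence is confined to descriptive safety tables; the primary endpoint is untouched.

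There is also a cross-reference error. Table 9 keys the Day 15 vital-sign mark to footnote w, which in that table concerns urine dipstick, while the BP rule is in footnote d. On its own this is clerical, but it leaves unclear whether subjects attending for proteinuria also contribute Day 15 vital signs, which would be a second form of selection.

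**What to change.** 1. In SAP 5.6.5 and Protocol 9.7.1.8.4, state that by-visit vital-sign summaries use only visits at which vital signs are required in all subjects: Baseline, Cycle 1 Day 1, Cycle 1 Day 15, Day 1 of each later cycle, and Off-Tx.
2. Report Day 15 readings from Cycle 2 on in listings, or in a separate table with n, labelled as the monitored subset.
3. Add a per-subject summary of worst post-baseline systolic and diastolic BP that uses all readings, including the Day 15 ones.
4. Reconcile the Table 9 Day 15 vital-sign mark (footnote w) with the BP rule in footnote d.

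The cost is a sentence or two of text, a visit filter and one extra table in the programs, and a corrected footnote letter. No new data are needed and patient management does not change.
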